7.4 Lost to Follow-up

A participant will be considered lost to follow-up if he or she repeatedly fails to return for scheduled visits and is unable to be contacted by the study center.

The following actions must be taken if a participant fails to return to the clinic for a required study visit:

- The study center must attempt to contact the participant and reschedule the missed visit as soon as possible and counsel the participant on the importance of maintaining the assigned visit schedule and ascertain whether or not the participant wishes to and/or should continue in the study.
- Before a participant is deemed lost to follow-up, the Investigator or designee must make every effort to regain contact with the participant (where possible, 3 telephone calls and, if necessary, a certified letter to the participant's last known mailing address or local equivalent methods). These contact attempts should be documented in the participant's medical record.
- Should the participant continue to be unreachable, he/she will be considered to have withdrawn from the study.

8.0 STUDY ASSESSMENTS AND PROCEDURES

Protocol waivers or exemptions are only permitted when necessary for the management of immediate safety concerns for the participant.

Immediate safety concerns should be discussed with the Sponsor as soon as they occur or when the study team becomes aware of them. The purpose of this communication is to determine if the participant(s) should discontinue the study intervention.

Study procedures and their timing are summarized in the SoA (refer to Section 1.3).

All screening evaluations must be completed, and the results reviewed before confirming that potential participants meet all eligibility criteria.

The Investigator will maintain a log of all participants screened. All relevant information, such as confirmation of eligibility and reasons for screening failure will be mentioned in this screening log.

The Study Reference Manual provides the Investigator and study center personnel with detailed administrative and technical information that does not impact the participant safety.

8.1 Immunogenicity Assessments

8.1.1 Biological Samples

Biological samples will be used for research planned in the protocol and for purposes related to the improvement, development and quality assurance of the laboratory tests described in this protocol or in future protocols part of the same development plan. The details of samples for immunogenicity assessments are shown in [Table 8](#).

Findings in this or future studies may make it desirable to use samples acquired in this study for research not planned in this protocol. In this case, all participants in countries where this is allowed will be asked to give consent to allow GSK or a contracted partner, to use the samples for further research. The further research will be subjected to prior Institutional Review Boards (IRB)/Independent Ethics Committees (IEC) approval, if required by local legislation.

Information on further research and its rationale can be obtained from GSK.

Sample testing will be done in accordance with the recorded consent of the individual participant. No immunogenicity sample should be taken from participants that are discontinued or withdrawn from the study due to AEs or other reason.

By default, collected samples will be stored for a maximum of 20 years. This storage period begins when the last participant performs the last study visit. This timeline can be adapted based on local laws, regulations or guidelines requiring different timeframes or procedures. In all cases, the storage period should be aligned with participant's consent. These additional requirements must be formally communicated to, discussed, and agreed with GSK.

Table 8 Biological Sample

Sample type	Quantity	Unit	Time point	Participants sampled
Blood for serum preparation	Approximately 10 mL/Visit for antibody determination; approximately 15 mL/Visit for safety screening; up to 10 mL/Visit for pre/post-vaccination safety assays	mL	As scheduled (refer to Figure 1 and Table 1)	All participants in Stage 1 and Stage 2
	Approximately 20 mL/Visit for assay development			Only participants in Stage 1 who have given specific consent for this collection
Blood for PBMC preparation	Approximately 50 mL/Visit for PBMC extraction for monoclonal antibodies generation			All participants in Stage 2

Abbreviation: PBMC = peripheral blood mononuclear cells

8.1.2 Laboratory Assays

All laboratory testing will be performed using characterized and fit-for-purpose qualified assays as indicated in [Table 9](#) at GVGH laboratory or in a laboratory designated by GVGH.

Table 9 **Laboratory Assays**

Assay type	System	Sampling time points	Component	Method	Unit of measure	Number of participants
Humoral Immunity (Antibody determination)	Serum	Stage 1 Days 1, 29, 57, 85, 169 and 197	Anti- S. Typhi Vi Ag total IgG	ELISA	EU/mL [#]	50 (Stage 1) 105 (Stage 2)
		Stage 2 Days 1, 29, 57, 85, 169 and 197	Anti- S. Typhimurium O Ag total IgG		EU/mL	
			Anti- S. Enteritidis O Ag total IgG		EU/mL	
Clinical Safety	Whole blood	Screening: Day -28 to Day -1 Stage 1 Days 1, 8, 29, 57, 64, 85, 169, 176 and 197 Stage 2 Days 1, 8, 29, 57, 64, 85, 169, 176 and 197	Leukocytes (white blood cells) Eosinophils Basophils Neutrophils Monocytes Lymphocytes Erythrocytes (red blood cells) ^s Hemoglobin Hematocrit ^s Platelets Prothrombin time ^{s, **}	Hematology panel		155 (Screening) 50 (Stage 1) 105 (Stage 2)
	Serum/whole blood	Screening: Day -28 to Day -1 Stage 1	Total bilirubin ^s Aspartic Aminotransferase Alanine Aminotransferase γ-Glutamyl Transferase ^s	Biochemistry		155 (Screening) 50 (Stage 1) 105 (Stage 2)

Assay type	System	Sampling time points	Component	Method	Unit of measure	Number of participants
		Days 1, 8, 29, 57, 64, 85, 169, 176 and 197 Stage 2 Days 1, 8, 29, 57, 64, 85, 169, 176 and 197	Lactic Dehydrogenase ^s Alkaline Phosphatase ^s Total Proteins ^s Glycosylated hemoglobin (HbA1c) ^s Urea/Blood Urea Nitrogen Creatinine Sodium ^s Potassium ^s			
	Serum	Screening: Day -28 to Day -1	HBsAg HCV antibodies HIV antibodies	Serology for virology		155 (Screening)
	Urine	Screening: Day -28 to Day -1 Stage 1: Days 1, 57 and 169 Stage 2: Days 1, 57 and 169	Human chorionic gonadotropin	Pregnancy test		NK (Stage 1) NK (Stage 2)
	Urine	Screening	Urinalysis	Dipstick		155 (Screening)
	Serum	Screening	Human leukocyte antigen B27*	PCR		50 (Stage 1, Screening)

Abbreviations: Ab = Antibody; CCI [REDACTED]; IgG = Immunoglobulin G; EU = ELISA Units; ELISA = enzyme-linked immunosorbent assay; GVGH = GlaxoSmithKline Biological SA Vaccines Institute for Global Health; HBsAg = hepatitis B surface antigen; HCV = hepatitis C virus; HIV = human immunodeficiency virus; NK = Not Known; PCR = polymerase chain reaction; ^s = test performed only during Screening period; CCI [REDACTED]; CCI [REDACTED]

The IgG against Vi antigen will be determined using GVGH ELISA and the results will be presented in EU/mL unit, which may be further converted to µg/mL, based on correlation with concentration of the standard calibrated against the international standard/another standard already calibrated.

* The assay will be performed by the site laboratory, or a laboratory designated by the site. In case of participant rescreening, this test should not be repeated since the result is not expected to change in the participant lifetime.

**Prothrombin time will only be applicable for Stage 1 participants.

8.2 Safety Assessments

The primary safety endpoints will assess the occurrence of laboratory abnormal values, solicited administration site and systemic events 7 days following each study intervention administration, unsolicited AEs which occur within 28 days after each study intervention administration and SAEs throughout the study duration. The occurrence of withdrawals due to AEs will also be assessed throughout the study duration. Currently, there are no AEs of special interest foreseen in this study.

Grading of laboratory values will be based on the US Food & Drug Administration Guidance for Industry “Toxicity Grading Scale for Healthy Adults and Adolescent Volunteers Enrolled in Preventive Vaccine Clinical Trials” [\[US Department of Health and Human Services, 2007\]](#) and Division of AIDS Table for Grading the Severity of Adult AEs [\[US Department of Health and Human Services, 2017\]](#). Refer to [Appendix 7](#).

Planned time points for all safety assessments are provided in the SoA ([Table 1](#)).

8.2.1 Pre-intervention Administration Procedures

8.2.1.1 Collection of Demographic Data, Medical/Vaccination History, and Physical Examination

Demographic data such as age in years, sex, and race (ethnic background) will be collected from each participant. Collection of sex and race (ethnic background) data is necessary to assess and monitor the diversity of the trial participants, and to determine if the trial participants are truly representative of the impacted population and the impact of race (ethnic background) on the trial endpoints. Medical history should be collected, and it should be verified that none of exclusion criteria related to medical and vaccination history (refer to Section [5.2](#)) are met. Vaccine history will be recorded for each participant. Physical examination will be performed for each participant. Physical examination includes assessment of body temperature (axillary) and resting vital signs (systolic/diastolic blood pressure, heart rate, and respiratory rate). On days of vaccination, body temperature and vital signs will be measured before and 60 minutes after vaccination. If the Investigator determines that the participant’s health on the day of the study intervention administration temporarily precludes dosing, the visit will be rescheduled.

8.2.1.2 Pregnancy

- Details of all pregnancies in female participants will be collected after the start of study treatment and 1 month after completion of the last study intervention administration.

- If a pregnancy is reported, the Investigator should inform the Sponsor within 24 hours of learning of the pregnancy and should follow the procedures outlined in [Appendix 4](#).
- Abnormal pregnancy outcomes (eg, spontaneous abortion, fetal death, stillbirth, congenital anomalies, ectopic pregnancy) are considered SAEs.

Generally, follow-up will be no longer than 6 to 8 weeks after the estimated delivery date. Pregnancy termination will be reported regardless of fetal status (presence or absence of anomalies) or indication for procedure.

8.2.2 Clinical Safety Laboratory Assessments

All laboratory testing will be performed at GVGH laboratory or in a laboratory designated by GVGH. Please refer to [Table 9](#) for the list of clinical laboratory safety assessments required by the protocol.

The Investigator may perform additional tests, if considered essential for the participant's safety.

8.3 Adverse Events

The definitions of an AE or SAE can be found in [Appendix 3](#).

Adverse events will be reported by the participant (or, when appropriate, by a caregiver, surrogate, or the participant's legally authorized representative).

The Investigator and any designees are responsible for detecting, documenting, and recording events that meet the definition of an AE or SAE and remain responsible for following up AEs that are serious, considered related to the study treatment or study procedures, or that caused the participant to discontinue the study intervention (refer to Section [7.0](#)). For further details, please refer to [Appendix 3](#).

8.3.1 Time Period and Frequency for Collecting AE and SAE Information

The definition of an AE or SAE are provided in [Appendix 3](#). All initial SAEs will be recorded and reported to the Sponsor or designee immediately, without undue delay but not later than within 24 hours of obtaining knowledge, as indicated in [Appendix 3](#). The SAEs will be reported for every participant throughout the study until study end (Day -28 to Day 337).

The Investigator or designee will record and immediately report all SAEs in screened and enrolled participants to the Sponsor or designee via the Expedited AE Reporting Form. Reporting should, under no circumstances, occur later than 24 hours after the Investigator becomes aware of an SAE. The Investigator will submit any updated SAE data to the Sponsor within 24 hours of it being available.

Investigators are not obligated to actively seek AE or SAE after conclusion of the study participation. However, if the Investigator learns of any SAE, including a death, at any time after a participant has been discharged from the study, and he/she considers the event to be reasonably related to the study treatment or study participation, the Investigator must promptly notify Sponsor or Sponsor's delegate.

8.3.2 Method of Detecting AEs and SAEs

The methods for detecting and recording AEs and SAEs, and the assessment of AE/SAE intensity, causality, and outcome are provided in [Appendix 3](#).

Care will be taken not to introduce bias when detecting AEs and/or SAEs. Open-ended and non-leading verbal questioning of the participant is the preferred method to inquire about AE occurrences.

After the initial AE/SAE report, the Investigator is required to proactively follow each participant at subsequent visits/contacts. All SAEs will be followed until resolution, stabilization, the event is otherwise explained, or the participant is lost to follow-up. Further information on follow-up procedures is given in [Appendix 3](#).

8.3.2.1 Clinically Significant Abnormal Laboratory Findings

The Investigator must review the laboratory report, document that he/she did so, and record any clinically relevant changes occurring during the study in the AE section of the eCRF. Clinically significant abnormal laboratory findings are those which are not associated with an underlying disease, unless judged by the Investigator to be more severe than expected for the participant's condition.

All clinically significant abnormal laboratory test values reported during the study will be repeated until the values return to normal/baseline, or until they are no longer considered significantly abnormal by the Investigator.

If such values do not return to normal/baseline after an interval judged reasonable by the Investigator, the etiology of the abnormal value should be identified, and the Sponsor notified.

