An additional 20 mL for assay development will be taken in Stage 1 on Day 85 from the participants who have given specific consent.

§ Out-of-window vaccination is not allowed.

¹ For literate participants in Europe/Africa only

² For illiterate participants in Africa only

³ The pre 2nd and 3rd vaccination screening in Malawi could take more than a day, necessitating additional site visits but not more than 72 hours prior to the actual receipt of the vaccination.

⁴ For illiterate participants, pDiary cards will be completed by the site field worker.

⁵ For illiterate participants, pDiary cards can be returned by the field worker at the end of the 7 days after administration.

⁶ For Malawi (Stage 2) only, subjects who test positive for malaria at Screening will be temporarily excluded (even if asymptomatic) and enrollment/first vaccination delayed until a negative malaria highly sensitive RDT is available. Treatment will also be provided for such prospective participants at the Investigator's discretion according to local guideline. For subsequent vaccinations, malaria RDT testing will only be performed if participants have symptoms suggestive of malaria.

⁷ Home visit for safety follow-up will take place only on Day 2.

Table 2 Intervals Between Study Visits

Interval	Planned visit interval	Allowed interval range
Screening (Day -28) → Visit 1 (Day 1)	Up to 28 days*	Up to 28 days*
Visit 1 (Day 1) → Visit 2 (Day 8)	7 days	7-10 days
Visit 1 (Day 1) → Reminder phone call 1 (Day 4)	3 days	1-3 days
Visit 1 (Day 1) → Visit 3 (Day 29)	28 days	28-33 [#] days**
Visit 1 (Day 1) → Visit 4 (Day 57)	56 days	52-62 days**
Visit 4 (Day 57) → Visit 5 (Day 64)	7 days	7-10 days
Visit 4 (Day 57) → Reminder phone call 2 (Day 60)	3 days	1-3 days
Visit 4 (Day 57) → Visit 6 (Day 85)	28 days	28-33 [#] days**
Visit 4 (Day 57) → Visit 7 (Day 169)	112 days	110-126 days**
Visit 4 (Day 57) → Visit 7 (Day 169)	112 days	110-140 ^{\$} days**
Visit 7 (Day 169) → Visit 8 (Day 176)	7 days	7-10 days
Visit 7 (Day 169) → Reminder phone call 3 (Day 172)	3 days	1-3 days
Visit 7 (Day 169) → Visit 9 (Day 197)	28 days	28-33 [#] days**
Visit 7 (Day 169) → Visit 10 (Day 337)	168 days	154-182 days

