5.5 Criteria for Temporarily Delaying Enrollment/Study Intervention Administration

Enrollment/study intervention administration may be postponed within the permitted time interval until transient conditions cited below are resolved:

- Participants with hematological/biochemical values out of normal range (and deemed clinically significant by the Investigator) as per the latest available test result, which are expected to be temporary may be rescreened/re-dosed at a later date within the allowed time interval (The latest laboratory results will be used to assess eligibility for second and third study intervention administration).
- Acute disease or fever at the time of enrollment and/or study intervention administration.
- Refer to the SoA ([Table 1](#)) for definition of fever and preferred location for measuring temperature in this study.
- Participants with a minor illness (such as mild diarrhea, mild upper respiratory infection) without fever may be enrolled and/or dosed at the discretion of the Investigator.
- Use of antipyretics and/or analgesics and/or antibiotics within 3 days prior to study intervention administration.
- Participants with a positive COVID-19 test in the 14 days before a planned study intervention administration will be allowed to receive the study intervention at least 14 days after the date of their first positive COVID-19 test.

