6.5. BASELINE

Baseline is defined as the last scheduled measurement taken prior to vaccination and will correspond to:

- Day 1 pre-dose for seroresponse calculation (4-fold for Anti-serotype specific IgG and \geq CCI for Anti-S. Typhi Vi Ag IgG antibody concentrations and GMR)
- Each vaccination pre-dose for immunogenicity within-participant GMR assessments, hematology, biochemistry and vital signs.

If a participant is missing the planned individual vaccination pre-dose result, change from baseline will not be calculated for within-participant GMR, hematology and biochemistry.

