16.2. SAFETY LABORATORY EVALUATIONS

Laboratory results will be included in the reporting of this study for Hematology and Biochemistry. A list of laboratory assessments to be included in the outputs is included in Table 9 of the protocol.

For each group and for each haematology and biochemistry parameter:

- The percentage of participants having hematology and biochemistry results below/within/ above the local laboratory ranges versus baseline will be tabulated by treatment, timepoint and stage.
- The percentage of participants with hematology and biochemistry results by grade versus baseline will be tabulated by treatment, timepoint and stage.

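### SAP 6.5 takes the last scheduled laboratory value as baseline, so a clinically significant result before dose 2 or 3 that is repeated off schedule and clears before dosing stays the baseline after it has been superseded

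*Protocol*

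**What the plan says.** **Repeats.** Protocol 8.3.2.1: "All clinically significant abnormal laboratory test values reported during the study will be repeated until the values return to normal/baseline". Repeating may also stop once the investigator no longer judges the value significant.

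**Dosing.** Under Protocol 5.5, participants with out-of-range values that the investigator deems clinically significant and "which are expected to be temporary may be rescreened/re-dosed at a later date within the allowed time interval". The same item adds: "The latest laboratory results will be used to assess eligibility for second and third study intervention administration". It does not restrict this to scheduled samples.

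**Timing.** Table 1 in Protocol 1.3 places the pre-dose safety samples at Visits 4 and 7, the visits for doses 2 and 3. Its third footnote says: "The pre 2nd and 3rd vaccination screening in Malawi could take more than a day". Extra site visits are allowed up to 72 hours before the vaccination.

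**Baseline.** SAP 6.5: "Baseline is defined as the last scheduled measurement taken prior to vaccination and will correspond to", in its second bullet, "Each vaccination pre-dose for immunogenicity within-participant GMR assessments, hematology, biochemistry and vital signs". It adds that no change from baseline is calculated for hematology or biochemistry if the planned pre-dose result is missing.

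**Use of baseline.** SAP 16.2 plans two laboratory tables, both against baseline. One shows the range category (below, within, above). Of the other it says: "The percentage of participants with hematology and biochemistry results by grade versus baseline will be tabulated by treatment, timepoint and stage". Two grading rows in Protocol Appendix 7 also use the participant's own baseline: hemoglobin change (Table 19, Stage 1) and the creatinine multiple (Table 20, Stage 2).

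Neither document says whether a repeated pre-dose value replaces the scheduled one.

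**The concern.** A participant can be cleared for dose 2 or 3 on one laboratory value and analyzed against another. Repeats are triggered by an abnormal value and stop on recovery, so the value that SAP 6.5 sets aside is normally the better of the two.

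Two distortions follow. An abnormality that clears before the dose and returns after it is tabulated as present at baseline. A value that clears and stays normal is tabulated as an improvement after vaccination. Laboratory deviations are a primary safety endpoint in this first-in-human study. With 45, 45 and 15 participants in the Stage 2 groups, one or two misclassified shifts would be visible in a table.

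**Working it through.** No stated figure has to be reproduced. The check has four steps.

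**1. Is there time for a repeat before the dose?** Room = latest allowed day minus planned day (Protocol Table 2).

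| Dose | Planned interval | Latest allowed | Room |
|---|---|---|---|
| 2 | 56 days | 62 days | 62 − 56 = 6 days |
| 3, Stage 1 | 112 days | 126 days | 126 − 112 = 14 days |
| 3, Malawi | 112 days | 140 days | 140 − 112 = 28 days |

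So a postponed dose after a repeat fits the windows. Pre-dose work over several days is described for Malawi only.

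**2. Does the SAP wording exclude the repeat?** Baseline is limited to scheduled measurements, and a missing planned result leaves the change uncalculated. Read together, an unscheduled value does not stand in for the planned one.

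**3. What do the tables then show?** The values below are illustrative assumptions, and each scheduled value is assumed to have been judged clinically significant. Cut-offs are those of Protocol Tables 19 and 20.

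| Case | Scheduled pre-dose | Repeat | Post-dose | Against scheduled value | Against repeat |
|---|---|---|---|---|---|
| ALT, Stage 2 (× ULN) | 3.0 | 0.9 | 2.8 | above to above; Grade 2 to Grade 2 | within to above; ungraded to Grade 2 |
| Hemoglobin change, Stage 1 female (g/dL) | 10.8 | 12.8 | 10.7 | fall 10.8 − 10.7 = 0.1: Grade 1 | fall 12.8 − 10.7 = 2.1: Grade 3 |
| Creatinine, Stage 2 (× ULN) | 1.2 | 0.75 | 1.2 | ratio 1.2/1.2 = 1.0: Grade 1, from the ULN criterion only | ratio 1.2/0.75 = 1.6: Grade 3 |

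In the hemoglobin case the post-dose 10.7 g/dL is also Grade 2 on the separate absolute row for females (9.5 to <11.0). If the higher of the two rows were reported, the result would be Grade 2 instead of Grade 3. If the ALT had stayed at 0.9 × ULN after the dose, the SAP table would show Grade 2 to ungraded, an apparent improvement; against the repeat there is no change.

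**4. How many?** The documents give no repeat rate. There are 155 × 2 = 310 planned pre-dose panels before doses 2 and 3, all groups included. An assumed repeat rate of 2 to 5% gives 310 × 0.02 = 6.2 to 310 × 0.05 = 15.5, about 6 to 16 panels. For Malawi alone, 105 × 2 = 210 panels give 4.2 to 10.5, about 4 to 11. These count repeats. A masked new abnormality also needs the repeat to clear and the value to become abnormal again after the dose, so at any given repeat rate the masked cases are fewer.

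**The case against.** **The repeat may count as the scheduled sample.** Visits 4 and 7 are themselves the dosing visits, and Protocol 8.2.1.1 reschedules the visit when the participant's health that day precludes dosing. If the sample at the rescheduled visit is recorded as Visit 4 or 7, SAP 6.5 picks the right value and the problem disappears. This stands as a possibility, but neither document states it.

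**The trigger is narrow.** Only clinically significant values must be repeated. If the pre-dose sample is drawn on the dosing day and reported later, clearance rests on an earlier result, the scheduled sample is the most recent one, and baseline is correct. This stands and limits the reach.

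**Nothing abnormal disappears.** A reader might infer that the rule hides new abnormalities and makes the primary laboratory results look better overall. The documents do not support that. The endpoint counts deviations from normal or from baseline, and Protocol Table 11 plans out-of-range percentages by time point, which need no baseline. SAP 16.2 still shows the post-dose category and grade, and clinically relevant changes are recorded as adverse events. The maximum-grade table in Protocol Table 11 is a weaker safeguard: SAP 16.2 does not list it, and its hemoglobin and creatinine grades may use the same baseline.

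**The remedy has its own bias.** Only abnormal values are retested, so using repeats replaces some high or low baselines selectively. Regression to the mean may then slightly increase apparent worsening after the dose. This is true but small, and does not justify comparing against a value already superseded when the dose was given.

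**The stakes are descriptive.** No hypothesis is tested, and SAP 16 plans no statistical comparison of safety between groups. This limits the severity, but shift tables are read descriptively and should use the right starting value.

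**Conclusion.** The gap is in SAP 6.5; the protocol's repeat rule contains no error. The SAP wording can set a post-dose result against a value superseded before dosing when three conditions hold: the scheduled Day 57 or Day 169 result is known before the dose, it is judged clinically significant, and the repeat is recorded as unscheduled. This is most plausible in Malawi.

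The loss is specific. Both SAP 16.2 tables can miss that an abnormality is new since the dose, or show an improvement that preceded it. The Stage 1 hemoglobin-change row and the Stage 2 creatinine row can be under-graded.

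The number of participants affected cannot be estimated from the documents. A reader might take 6 to 16 as the count of masked abnormalities. It is the number of repeated panels at an assumed 2 to 5% rate, and only an upper bound on masked cases at that rate. The point is worth correcting, but it does not put the overall laboratory safety results in doubt.

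**What to change.** In SAP 6.5, for hematology and biochemistry only, define baseline as the last valid value before the vaccination concerned, scheduled or unscheduled. Use it in both SAP 16.2 tables and in the two baseline-dependent grading rows. Vital signs need no change, because SAP 16.3 summarizes observed values only.

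Add a listing that shows the scheduled and the repeat value side by side wherever a pre-dose panel was repeated. This lets a reader judge any regression to the mean.

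The cost is one phrase in the SAP, the matching derivation and one short listing. It uses data already collected and alters no rule on retesting or dosing.
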